6.1 Design

This is a single-centre randomised feasibility study evaluating the impact of different completion rates of DSME programmes on psychometric outcomes specifically looking at ability to self-care, diabetes distress and quality of life. DSME will be the intervention and will typically be delivered within 3 weeks of the baseline appointment. There is a deliberate short separation between education intervention and follow up psychometric tests of 3-4 months to allow participants the opportunity to adopt any behaviour changes following the DSME programme whilst minimising the risk of not receiving the full NICE recommended DSME programme and to broadly align with landmark studies. Landmark studies namely DCCT (26,27) and DESMOND (25) evidenced a statistically

significant improvement to PROMs at 4 months post education intervention, however HbA_{1c} changes were not significant within this timeframe despite being statistically powered. A recent systematic review (38) concluded that as DSME is primarily focused on behavioural change to facilitate glycaemic control, efficacy measures should focus on behavioural and psychosocial changes, however these are often overlooked. This study is a feasibility trial and by its very nature is not statistically powered, therefore despite HbA_{1c} being arguably the measure of choice within the literature for measuring effectiveness of diabetes interventions, this study will use PROMs as its primary outcome measure.

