Intervention • How is the intervention different from normal care? • What does it look like? • Is it clear when it starts and finishes?	Clinical intervention of participants will not be altered. Participants will receive the same DSME programme as routine clinical patients. Normal delivery of DSME programmes is by a diabetes specialist nurse or dietitian. Research DSME programmes will be, where possible, delivered by the researcher for consistency. Participants will be reminded at the beginning of the DSME programme that this is a research study and that some participants will leave after 36 minutes, 3 hours and 36 minutes, with others remaining for the full 6 hours programme. Reminders will be given at the time points in which participants from groups 2 and 3 should leave.
Contextual information • Policy initiatives related to the intervention?	DSME is NICE recommended for all patients newly diagnosed with type 2 diabetes with annual refresher thereafter (15). The National Diabetes Audit suggests 71% of people with type 2 diabetes are offered DSME, with an average attendance rate of 7%. Local records suggest that of those that start DSME (9%) only 12.6% complete the programme (20).

Visit 3

Between 3-4 months post intervention participants will be asked to repeat baseline psychometric tests. For participants in group 4 this will be 4 months from enrolment. This will be the end of the study.

At the end of the study participants in groups 2, 3 and 4 will be offered a full DSME programme.

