6.4 Data Analysis

Descriptive analysis will be completed for all demographic data presenting continuous variables as means \pm standard deviation and categorical variables as numbers (%). Data will be tested for normality using a Shapiro-Wilk test and subject to visual inspection of histograms and normal Q-Q plots.

Psychometric outcomes will include the Diabetes Self-Management Questionnaire-Revised (DSMQ-R)(48), Problem Areas in Diabetes (PAID) scale (49) and the Patient reported outcome measures information system (PROMIS) Global Health scale v1.2 (50). Data will be treated as continuous and analysis of the difference in the mean before and after intervention will be conducted using an analysis of variance (ANOVA) test to check for statistical and clinical difference in the mean across the four groups.

Statistical analysis will be conducted using IBM® SPSS® Premium 29 with support from University of Liverpool statisticians. The alpha level will be set at 5% for statistical significance.

Whilst a statistically significant difference is desirable, it is important to understand what would represent a meaningful clinical change for a patient. As such the minimal clinically important difference (MCID) will be reported to measure the smallest difference in which the patient would perceive a benefit (61–64). Where the MCID is not published this will be calculated using a distribution-based derivation using 0.5 SD of the observed change in PROM score (62,65). Whilst this approach is not without its limitations (61,63) no consensus on the ideal means of determining the MCID is available (63). A systematic review concluded that 0.5 SD of the observed change approximated the published MCID in the majority of cases popularising this derivation in the literature (65).

MCID will be classed as >2 T-score points for the PROMIS Global Health v1.2 (66) in which physical health and mental health are given separate T-scores with a 95% confidence interval. The MCID will be calculated for PAID and DSMQ-R.

Recruitment of participants and the number of dropouts will be reported descriptively (frequencies and percentages). Due to the aims of this study considering differing completion levels of DSME, intention to treat analysis will not be used. Where participants allocated to a group do not fully complete the required amount of DSME there results would be withdrawn from the final analysis.

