8.2 Recruitment

8.2.1 Sample Size

A sample size of 24-50 participants per group is deemed adequate within a feasibility study to estimate effect sizes and inform future DSME modifications and research (68,69). A sample of 120 patients will be enrolled onto this study allowing for adequate numbers (n=30) across the four groups, controlling for expected participant drop out. Monthly recruitment targets are pre-specified in a study progression criteria table (table 3) to ensure an adequate sample size is achieved for data analysis.

The diabetes outpatient department receives on average 24 referrals for DSME per month with a mean monthly attendance rate of 21 patients. Locally an average of 86 patients are newly diagnosed with type 2 diabetes each month (20), patients who have opted in for data sharing are contacted with an offer of DSME. This has been used to inform realistic recruitment rates. Recruitment rates will be kept under review and discussed with supervisors should the monthly figure fall below projected numbers.

Table 3:Progression criteria and study status

Criterion	Green	Amber	Red
Monthly recruitment	≥ 17 participants	14-16 participants	< 13 participants
Retention rate	>80% at endpoint	60-80% at endpoint	<60% at endpoint

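### Groups 1-3 are taught in shared sessions and Group 4 in none, but the ANOVA in 6.4 treats everyone as independent: the standard error is likely modestly too small for at least one comparison with Group 4, and no session ICC is planned

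*Combined protocol and SAP*

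**What the plan says.** **Delivery.** Section 6.2 (Visit 1) has the research sessions run apart from routine education, so that people leaving part way do not disturb ordinary patients. Groups 1-3 book a session, typically within 3 weeks of enrolment. Table 2 in 6.2 says participants will be reminded that "some participants will leave after 36 minutes, 3 hours and 36 minutes, with others remaining for the full 6 hours programme". The three groups therefore start in the same room. Group 4 is not required to attend. On who teaches, Table 2 says: "Research DSME programmes will be, where possible, delivered by the researcher for consistency".

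**Analysis.** Section 6.4 says that analysis of the difference in means before and after the intervention "will be conducted using an analysis of variance (ANOVA) test to check for statistical and clinical difference in the mean across the four groups", and adds: "The alpha level will be set at 5% for statistical significance". It contains no session term, random effect, cluster-robust error or ICC.

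**Size and purpose.** Section 8.2.1 states: "A sample of 120 patients will be enrolled onto this study allowing for adequate numbers (n=30) across the four groups". Its basis is a rule of thumb: "A sample size of 24-50 participants per group is deemed adequate within a feasibility study to estimate effect sizes". Section 6.1 says the study "by its very nature is not statistically powered". The Abstract lists eligibility, recruitment and retention as the feasibility measures, and the stated purpose is to test whether a full randomised trial is feasible.

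**The concern.** People taught in one session share discussion, date and usually a teacher, so their outcomes may be correlated. One-way ANOVA assumes that they are not. Three arms share sessions and the fourth has none, so this is a partially clustered design.

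Two things are at stake. First, confidence intervals and p-values for comparisons with the no-education group would look more precise than they are. Second, a full trial of group-delivered education needs some assumption about session clustering. This study generates the relevant data but plans no such output.

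**Working it through.** **Inputs from the documents.** 120 participants in four groups of 30 (8.2.1); green recruitment of at least 17 a month (Table 3); sessions typically within 3 weeks of enrolment; participants book, with no balancing of groups within sessions described (6.2). The block ratio of 2:1 in 6.2 does not fit four groups of 30, so equal groups are used here.

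**Plan's own figure.** 4 × 30 = 120. If 20% dropout is assumed, 24/(1 − 0.20) = 30, so 30 per group matches the lower end of 24-50.

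**Assumptions.** The documents give neither session size nor ICC. At 17 recruits a month, Groups 1-3 gain 17 × 0.75 = 12.75 a month. One session every 3 weeks (assumed) gives 12.75 × 3/4.33 ≈ 8.8 people, about 3 per group, hence about 90/8.8 ≈ 10 sessions. Six sessions of 15 (5 per group) is the alternative. The session ICC ρ is taken as 0.05 to 0.10, with 0.20 as an upper case.

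**Against Group 4.** Let total variance be 1 in every arm, K the number of sessions, and m = 30/K the number per group per session. For an arm with session ICC ρ:

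- Balanced sessions: true variance of the difference = [2 + (m − 1)ρ]/30.
- Random booking: true variance = [2 + 29ρ/K]/30.
- ANOVA reports (2/30) × MSE. MSE is 1 − 0.75(m − 1)ρ/29 if balanced and 1 − 0.75ρ/K if booked.

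Example, K = 10, ρ = 0.10, balanced: (2 + 0.2)/30 = 0.0733; MSE = 1 − 0.75 × 0.2/29 = 0.9948; reported variance 0.0663; ratio of standard errors √(0.0733/0.0663) = 1.05. Type I error is 2[1 − Φ(1.96/ratio)].

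| Sessions | ρ | Balanced: true/reported SE (type I) | Booked: true/reported SE (type I) |
|---|---|---|---|
| 10 | 0.05 | 1.026 (5.6%) | 1.038 (5.9%) |
| 10 | 0.10 | 1.052 (6.2%) | 1.074 (6.8%) |
| 6 | 0.05 | 1.052 (6.2%) | 1.062 (6.5%) |
| 6 | 0.10 | 1.101 (7.5%) | 1.121 (8.0%) |

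Simulation with 30 per arm agrees within its own error: 1.02 to 1.13 for Group 1 v Group 4 across these settings. At ρ = 0.20 the ratio reaches about 1.10 to 1.23. If Group 4 is instead given the lower variance 1 − ρ, the ratio with a common effect is 0.987 to 0.999 at m = 1 and 1.001 to 1.014 at m = 2 (ρ of 0.01 to 0.10). Hence the condition of about two or more per group per session.

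**Which arm is affected.** The table applies to all three taught arms if the session effect is the same for all. Suppose instead that it scales with time in the room (1, 0.6, 0.1 for Groups 1, 2, 3; assumed). Group 1's figures stay, but Group 3's ICC becomes 0.1² × ρ, so at m = 5 and ρ = 0.10 the ratio is about √(1 + 4 × 0.001/2) = 1.001. The error for Group 3 v Group 4 vanishes.

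**Among Groups 1-3** (10 sessions, ρ = 0.05 and 0.10):

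- Common effect, balanced: true variance 2(1 − ρ)/30; ratio 0.98 and 0.95, so the reported error is too large.
- Common effect, random booking: true variance 2(1 − ρ/K)/30; ratio about 1.00, so it is about right.
- Scaled effect, balanced, Group 1 v Group 3: true variance [2 + 1.01(m − 1)ρ − 0.2mρ]/30; ratio about 1.02 and 1.04, so it is too small.

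**Precision of the ICC.** With an observed ICC of 0.05 and 10 sessions of 9, F = (1 + 8 × 0.05)/(1 − 0.05) = 1.47 on 9 and 80 degrees of freedom; the 95% interval is about −0.04 to 0.31. With 6 sessions of 15 it is about −0.02 to 0.40.

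**The case against.** **The effect is small and rests on assumed figures.** This stands. Neither the ICC nor the session size is in the documents, and in the central case (about 9 per session, ρ of 0.05 to 0.10) type I error is about 6 to 7%, in a study that disclaims power. The four-group F-test hardly moves: in simulation with 10 sessions it rejected in 4.7 to 6.4% of runs. The problem lies in the individual contrasts, which the stated aims (10% v none, 60% v 100%) call for.

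**One teacher limits clustering.** This stands in part. Using the researcher where possible reduces teacher effects, but not those of peers or date.

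**Session may already be recorded.** This is possible. The REDCap template and visit checklists are in appendices supplied separately, so the text does not settle it.

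**A stronger reading that does not hold.** A reader might infer that the errors run in opposite directions for the two aims: too optimistic for 10% v none and too pessimistic for 60% v 100%. That needs a session effect that is identical after 36 minutes, 3 h 36 min and 6 hours, and groups balanced within each session. The documents describe booking without balancing and very unequal exposure.

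**A second stronger reading.** A reader might also infer that this study could supply the ICC needed to size a full trial. An interval from about −0.04 to 0.31 informs that choice but cannot settle it.

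**Conclusion.** The concern holds in limited form. Groups 1-3 share sessions, Group 4 has none, and 6.4 assumes independence. If session correlation exists and about two or more participants per group share a session, the standard error is too small for at least one contrast with Group 4.

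For Group 1 v Group 4, with 30 per arm, 6 to 10 sessions and an assumed ICC of 0.05 to 0.10, the true standard error is about 2 to 13% larger than reported, with type I error about 5.6 to 8%. Group 3 v Group 4 is affected to a similar degree only under a common session effect; it is about right if the effect scales with exposure. Among Groups 1-3 the documents support no direction. Losses or exclusions that leave fewer per group per session would shrink these figures.

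This is a modest error in an unpowered study, worth correcting because it costs little.

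**What to change.** - **6.3 and the REDCap template:** make sure that a session number and deliverer are held for every Group 1-3 participant. If the template already has them, say so in 6.3. This is best settled before the first research session.
- **6.4:** analyse each PROM with a partially nested mixed model: a random session effect for Groups 1-3, none for Group 4, and small-sample degrees of freedom. Add a sensitivity analysis in which the session effect may differ by group, because a single common effect builds in the assumption that is in doubt.
- **Feasibility outputs:** report the session ICC with its confidence interval, as a descriptive result stated to be imprecise.

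**Cost:** two data fields and a slightly more complex model, with the statistical support that 6.4 already plans. With about 6 to 10 sessions the ICC will be poorly estimated and may come out at zero, so the text should not promise that it will size the full trial.

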Internationally the benchmark for recording a patient as completed DSME is attendance at $\geq 60\%$ of a programme's content (23,41–43), a discord with the literature measuring effectiveness of landmark studies at 100% completion (25,39). A record of DSME attendance is given for patients who sign up and engage with $>10\%$ of materials (23,41,43).

There is no research available measuring the impact of non-completion on UK DSME programme effectiveness or internationally on the impact of differing completion rates on patient reported outcome measures (PROMs) despite the acceptance of completion ($\geq 60\%$) at discord with legendary studies benchmarking completed at 100%. The aims of this study are to explore if patients who attend minimal aspects (10%) of DSME programmes gain clinically significant improvements in ability to self-care compared to those who do not attend, and if the nationally accepted 60 % completion rate is as effective as 100% completion.

THEORETICAL FRAMEWORK

Philosophical assumptions (also referred to as epistemology) influence our views about how phenomena should be approached (44) assisting researchers in refining the types of evidence required, how it should be collected, and how it should be interpreted. This quantitative study will adopt an experimental hypothesis driven design whereby the variable or intervention is controlled, with the exception of a control group, to attempt to establish causal effect of an intervention, in this case DSME completion rates. Whilst the most powerful and highly regarded form of experimental study remains the randomised control trial (RCT), this study will test the feasibility of conducting a full RCT.

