- Group 3: DSME 36 minutes, 10% of content (attended)
- Group 4: Delayed education (education not offered, not attended, or declined)

DSME programme overview is provided in appendix 1 giving a broad overview of DSME content by programme completion status. Local demographic data suggests that of the local population 46.4% are living in the most deprived neighbourhoods within the UK (9). Of the local population 19.3% have a reading age of 9-11 or below (53,54), are classed as being functionally illiterate and are therefore likely to struggle reading a paper questionnaire. Verbal support for completing the PROMs will be offered by the researcher to ensure participants from lower socioeconomic backgrounds are not excluded from participating in the DIABETES PRO study as they are evidenced to make up a larger proportion of people with diabetes (55-57). Support will be limited to reading the questions verbatim.

Participants will be asked to complete three psychometric tests measuring self-care activities, diabetes distress and quality of life using the following validated tools: Diabetes Self-Management Questionnaire-Revised (DSMQ-R)(48), Problem Areas in Diabetes (PAID) scale (49) and the Patient Reported Outcome Measures Information System (PROMIS) Global Health scale v1.2 (50) (appendix 1).

Participants in groups 1, 2 and 3 will be asked to book a DSME session with the researcher, typically this should be no longer than 3 weeks from study enrolment. Research group DSME programmes (intervention) will be run by the researcher separate to routine patient DSME to minimise disruption of participants leaving part way through on patients.

Participants randomised to group 4, delayed education will not be required to attend DSME as part of the DIABETES PRO study. Collected data will be collected and managed using Research Electronic Data Capture (REDCap) electronic data capture tools. A REDCap data collection tool has been included in Appendix 1 for reference. REDCap is a secure, web-based software platform designed to support data capture for research studies, providing an intuitive interface for validated data capture; audit trails for tracking data manipulation and export procedures; automated export procedures for seamless data downloads to common statistical packages; and procedures for data integration and interoperability with external sources (58,59) (see section 3.6 for further details).

Visit 2

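### The only planned comparison drops randomised participants who do not complete their allocated education, under a rule that is strictest in Group 1 and cannot apply to Group 4

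*Combined protocol and SAP*

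**What the plan says.** Section 6.4 (Data Analysis) sets the analysis population in two sentences. The first gives the reason: "Due to the aims of this study considering differing completion levels of DSME, intention to treat analysis will not be used". The second gives the rule: "Where participants allocated to a group do not fully complete the required amount of DSME there results would be withdrawn from the final analysis". The planned comparison is an ANOVA of pre-to-post change across the four groups at the 5% level. No as-allocated or sensitivity analysis is described.

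Section 6.2 (Visit 1) fixes the amounts: 6 hours (Group 1), 3 hours 36 minutes (Group 2) and 36 minutes (Group 3). For the control arm, "Participants randomised to group 4, delayed education will not be required to attend DSME as part of the DIABETES PRO study".

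Section 6.2 (Visit 3) sets the follow-up timing: "Between 3-4 months post intervention participants will be asked to repeat baseline psychometric tests", and "For participants in group 4 this will be 4 months from enrolment".

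Two statements show what the comparison is for. The Theoretical Framework says the design is meant "to attempt to establish causal effect of an intervention, in this case DSME completion rates". Section 8.2.1 says: "A sample size of 24-50 participants per group is deemed adequate within a feasibility study to estimate effect sizes".

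**The concern.** Randomisation makes the four groups comparable at allocation. The rule then removes people for something they do afterwards, and it does so unequally: the bar rises with the allocated amount, and nobody in Group 4 can fail it. If people who stay the course would have improved more anyway, the groups with the higher bar look better even when the education does nothing. If poorer responders stay longer, the distortion runs the other way.

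The stated reason does not require the rule. Completion level is the randomised factor, so comparing people as allocated still addresses differing completion levels, as the effect of being allocated each one.

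Three things are at stake:

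- **Effect estimates.** They are meant to inform later research. With non-completers removed, the results cannot show whether the bias is large or small.
- **Lost data.** Visit 3 is timed from the intervention in Groups 1-3, so someone who never attends has no Visit 3 date in the text. Scores not collected cannot be recovered.
- **A feasibility question left unnamed.** Dropouts and retention are reported, but the proportion in each arm receiving the allocated amount is not listed as an outcome.

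**Working it through.** **The plan's own figures.** 4 × 30 = 120 participants, as stated. 0.60 × 360 min = 216 min (3 h 36 min) and 0.10 × 360 = 36 min, as stated. The bars are 360, 216, 36 and 0 minutes.

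**Inputs.** From the documents: 30 per arm, alpha 5%, 24 as the lower end of the adequate range (8.2.1), and an MCID of 0.5 SD of observed change where none is published (6.4). Assumed, because the documents do not give them: completion in each arm, and a correlation ρ of 0, 0.3 or 0.5 between a latent tendency to complete and change in score. There is no true effect in any arm.

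**Model.** A participant with latent trait z completes if z exceeds the cut-off c that gives completion rate p. Change = ρz + √(1−ρ²)·e, in SD units. Among completers the mean shifts by ρ·φ(c)/p, where φ is the standard normal density.

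**One case in full: p = 0.70, 0.85, 0.95, 1.00.** The arm shifts at ρ = 0.3 / 0.5 are:

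- Group 1: 0.149 / 0.248
- Group 2: 0.082 / 0.137
- Group 3: 0.033 / 0.054
- Group 4: 0

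So Group 1 minus Group 2 is 0.067 / 0.111 SD, and Group 1 minus Group 4 is 0.149 / 0.248 SD.

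**All scenarios.** ANOVA rejection is from 8,000 simulated trials per cell; biases are closed-form, in SD, for ρ = 0.3 / 0.5.

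| Completion, Groups 1/2/3/4 | ANOVA rejection, ρ = 0 / 0.3 / 0.5 | Group 1−2 | Group 3−4 | Group 1−4 |
|---|---|---|---|---|
| 90/95/98/100% | 5.3 / 5.2 / 6.0% | 0.026 / 0.043 | 0.015 / 0.025 | 0.058 / 0.097 |
| 70/85/95/100% | 4.7 / 6.3 / 9.9% | 0.067 / 0.111 | 0.033 / 0.054 | 0.149 / 0.248 |
| 50/70/95/100% | 4.7 / 10.0 / 20.3% | 0.090 / 0.151 | 0.033 / 0.054 | 0.239 / 0.399 |
| 80/80/80/100% | 4.8 / 6.7 / 9.0% | 0 / 0 | 0.105 / 0.175 | 0.105 / 0.175 |

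The simulation standard error near 5% is √(0.05 × 0.95 / 8,000) ≈ 0.24 percentage points, so the ρ = 0 column is consistent with 5%. In a 6,000-trial run of the same scenarios, analysing everyone as randomised gave 4.7-5.6%.

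**Contrasts named in the aims.** For 100% versus 60%, t-test error is at most 7.6%. For 10% versus none, it is at most 9.7%, and that occurs in the 80/80/80/100% case.

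**Numbers left in Group 1.** The expected number is 30p, so 30 × 0.80 = 24 exactly meets the lower limit. The binomial probability of keeping at least 24 of 30 is 16% at p = 0.70, 61% at 0.80, 85% at 0.85 and 97% at 0.90. Losses at follow-up come on top: at 90% completion and 80% retention, 30 × 0.90 × 0.80 = 21.6. The local routine-care completion rate of 12.6% in the Background would leave 30 × 0.126 ≈ 3.8; that is an extreme bound, not a forecast for a trial.

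**The case against.** The study is explicitly unpowered and its outcomes are preliminary. On the two contrasts the aims name, the bias is at most about 0.15 SD (100% versus 60%) and 0.18 SD (10% versus none), well below 0.5 SD. The 20% error rate needs both 50% completion in Group 1 and a correlation of 0.5. The largest bias falls on Group 1 versus Group 4, which the aims do not name. All of this is correct and limits the size of the problem.

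The education may also be a single sitting in which some participants leave early. Most non-completion could then be non-attendance, affecting Groups 1-3 alike. In that case 100% versus 60% is unbiased, and the distortion is education versus delayed education. This also stands, and the documents do not settle which pattern will occur.

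The rule is a declared choice, and the amendment history shows that 6.4 was revised after ethics committee feedback. That makes it deliberate, but does not protect the comparison.

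The most substantial point is that as-allocated analysis has its own cost for the question whether 60% is as effective as 100%, because it pulls the arms together. As an illustration, assume true effects of 0.5 and 0.3 SD, no gain in non-completers, and 70% and 85% completion. The contrast becomes 0.5 × 0.70 − 0.3 × 0.85 = 0.35 − 0.255 = 0.095, against a true 0.20. That loss of 0.105 SD is comparable to the bias criticised here. It argues for presenting both analyses side by side for that aim, not for having only the filtered one.

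Finally, the rule withdraws results from analysis and does not itself stop collection. Partial attenders do have an intervention date; the Visit 3 gap concerns only those who never attend. The visit checklists are in a separate appendix and the flow chart could not be read, so a date may be given there.

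**Conclusion.** The concern holds. The text removes non-completers from three of four randomised arms, exempts the control arm by construction, and plans nothing to offset this, while stating a causal aim that an as-allocated comparison could serve.

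The size is conditional. Bias requires completion to be related to change in score. Given a correlation of 0.3-0.5, the four-group test has a false-positive rate of about 5-6% when completion is 90% or better, 6-10% at 70/85/95/100%, and 10-20% at 50/70/95/100%. Bias stays below 0.5 SD throughout and could reverse in direction. It may prove small, but the plan as written would not let anyone find out. A stated rule that can give a wrong answer in the only planned comparison, with possible permanent loss of follow-up data, must be corrected.

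**What to change.** - **Section 6.4:** make the primary analysis all randomised participants in the group assigned. Keep the completers-only analysis as a labelled supplementary analysis, and read the two together for 60% versus 100%.
- **Section 6.2, Visit 3, and Section 6.4:** seek the questionnaires from everyone, whatever they attended. For those in Groups 1-3 who never attend, time the visit from enrolment, as is already done for Group 4.
- **Section 6.4:** state how missing Visit 3 scores are handled, for example a baseline-adjusted model with a stated missing-data assumption and a sensitivity check, with missingness reported by arm.
- **Feasibility outcomes:** report the proportion receiving the allocated amount, by arm.

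The cost is an amendment to two sentences in 6.4 with the missing-data statement, one sentence added to the Visit 3 paragraph, sponsor submission and possibly ethics resubmission, and follow-up of non-completers with the same questionnaires. The primary estimate becomes the effect of being allocated an amount of education, so it is diluted as a measure of receiving it; the retained completers analysis is there for that question.
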